19.3.1. Serious Adverse Device Effect (SADE)

A serious adverse device effect is an adverse device effect that has resulted in any of the consequences characteristic of a serious adverse event or that might have led to any of these consequences if suitable action had not been taken or intervention had not been made or if circumstances had been less opportune.

Confidential Page 73 of 86

19.3.2. Unexpected Serious Adverse Device Effect (USADE)

Serious adverse device effect which by its nature, incidence, severity or outcome has not been identified in the current version of the risk analysis report.

Note: Expected serious adverse device effect is an effect which by its nature, incidence, severity or outcome has been identified in the IFU/IB.

19.4. Severity of Adverse Events

It is the Investigator's responsibility to assess the severity of an AE. A change in severity may constitute a new reportable AE. The following guideline should be used to determine the severity of each AE:

- MILD: Awareness of experience, but easily tolerated. No medical intervention required.
- **MODERATE:** Enough discomfort to interfere with usual activities. Medical intervention required.
- **SEVERE:** Inability to carry out usual activities. Medical intervention (including hospitalization or prolongation of hospitalization) required.

19.5. Relationship/Attribution of Adverse Events

It is the Investigator's responsibility to assess the relationship of an AE to the study procedure and study device(s).

The following guideline should be used in determining the relationship of an adverse event to the study device, study procedure, or other causality:

- Not related
- Unlikely
- Possible
- Probable
- Causal relationship.

19.6. Reporting Adverse Events

Enrollment through 30-Day Follow-Up: All adverse events (both serious and non-serious), whether attributable to the device/procedure or not, will be reported from time of enrollment, during the surgical procedure, and until completion of the 30-day follow-up. The Investigator will evaluate the severity of the event, and its relatedness to the study device or procedure and the information will be entered in the AE eCRFs.

6-Month Follow-Up:

Confidential Page 74 of 86

03 SEP 2019, VERSION: 1.1

Follow-up on all SAEs possibly related or related to study treatment, which were ongoing at the 30-day post-surgery follow-up will be assessed.

SAEs requiring surgical intervention and assessed as possibly related or related to the study treatment will be reported at the 6-month follow-up. The Investigator will evaluate the severity of the event, and its relatedness to the study device or procedure and the information will be entered in the AE eCRFs.

Any necessary medical management of the event will be recorded in the subject's medical record/source document.

The Investigator will record all AEs (both serious and non-serious) in the source documents. CTC (Common Terminology Criteria) should be used when recording AEs. In addition, the following information should be recorded:

- Onset date
- Resolution date or date of death
- Severity of the event
- Action taken
- Event status (ongoing at study end or resolved)
- Relationship of AE to the study treatment
- Relationship of AE to the study procedure
- Indication of seriousness.

19.6.1. Reporting Serious Adverse Events to the Sponsor

Enrollment through 30-Day Follow-Up:

The study site must report all SAEs, whether they are related to the device or procedure, to the Sponsor within 24 hours of becoming aware of the SAE.

6-Month Follow-Up:

The study site must report SAEs requiring surgical intervention and assessed as possibly related or related to the device or procedure to the Sponsor within 24 hours of becoming aware of the SAE.

The study site will report SAEs by entering the event into the EDC system via the Adverse Event eCRF, which will trigger an automated email to the Sponsor. Additional information, including the Investigator's assessment, may be added to the eCRF later; however, the study site must complete the AE eCRF within 24 hours of becoming aware of the SAE. If the Sponsor requires supporting documentation or other information, the Sponsor will contact the study site.

Confidential Page 75 of 86

ETHICON, LLC. BIOS_2017_02 03 SEP 2019, VERSION: 1.1

In the event of death, the Investigator must report all available information to the Sponsor.

The report of an SAE by a site does not constitute an admission that study personnel or the user facility (hospital/clinic) caused or contributed to the event. The study site is responsible for submitting AEs to the reviewing IRB/EC, per their IRB/EC procedures.

19.6.2. Reporting Non-Serious Adverse Events to the Sponsor

Enrollment through 30-Day Follow-Up:

All non-serious AEs, whether attributable to the device/procedure or not, will be reported from time of enrollment, during the surgical procedure, and until completion of the 30-day follow-up. For all non-serious AEs, the study site is expected to complete the Adverse Event eCRF within 2 weeks of becoming aware of the event. Supporting documentation may be requested, as needed.

19.6.3. Reporting Unanticipated Adverse Device Effects to the Sponsor

The study site must report all UADEs to the Sponsor within 24 hours of becoming aware.

Information not available at the time of the initial report (e.g., an end date for the UADE) must be updated within ______. In the event of a fatal or life-threatening event, any required follow-up information must be submitted to the Sponsor immediately, but no later than 10 calendar days of the initial report.

If the Sponsor determines an UADE presents an unreasonable risk to subjects, the Sponsor shall terminate all or a portion of investigations as soon as possible so as not to jeopardize the health of any subject.

Termination shall occur no later than 5 working days after the Sponsor makes this determination and no later than 15 working days after the Sponsor first receives notice of effect. Resumption of terminated studies can occur only with IRB/EC and Health Authority approval.

Other: The Investigator may also need to consider whether an event is attributable to the investigational product, based on insufficiencies or inadequacies in the instructions or as a result of user error. The Investigator must contact the Sponsor should this occur.

19.7. Product Complaint Definition

A product complaint is defined as any written, electronic or oral communication that alleges deficiencies related to the identity, labelling, quality, durability, reliability, safety,

Confidential Page 76 of 86

03 SEP 2019, VERSION: 1.1

effectiveness, or performance of a device after it is released for distribution. A product complaint may or may not be associated with an AE/SAE.

Product complaints may include, but are not limited to:

- Product contamination;
- Defective components;
- Poor packaging or product mix-up;
- Questionable stability;
- Device malfunction (the failure of a device to perform as intended for this study);
- Labelling concerns;
- User errors.

19.8. Reporting Product Complaints

Product complaints must be reported to the Sponsor in a timely manner. For all UADEs, the Sponsor must be notified within 24 hours of the site becoming aware. If an Ethicon representative is made aware of a product complaint related to the study device, the event should be reported within 24 hours of their awareness.

Product Complaint should be emailed to:

Global CHU: [contact]

Local CHU reporting: [contact]

20. DEVIATION FROM CLINICAL TRIAL PROTOCOL AND REGULATIONS FOR CLINICAL TRIAL PROTOCOL AMENDMENT

The study protocol deviations are defined as the circumstances that fail to comply with the requirements of clinical trial protocol intentionally or unintentionally.

All protocol deviations should be reported as protocol deviations to the Sponsor via the study EDC database. The reporting should include the date and reason for protocol deviations. The Investigator should also report the protocol deviations to the EC and all related department according to the site requirements and in combination with the requirements and procedures of the EC.

If a protocol amendment occurs, the Sponsor or designated person should submit a summary of changes of the study protocol to the Investigator, regulatory authority, and

Confidential Page 77 of 86

03 SEP 2019, VERSION: 1.1

the Ethics Committee, etc. according to the relevant laws and regulations. All major amendments must be approved by the Ethics Committee and regulatory authority (if needed) prior to implementing any changes to study procedures.

If an amendment likely has major impact on the following items, this amendment belongs to the major amendment:

- Safety or physical or mental health of subjects;
- Scientific value of trial;
- Implementation or management of trial;
- Quality or safety of investigational medical product specified in the trial.

21. DIRECT ACCESS TO SOURCE DATA AND DOCUMENT

The source data is defined as all information in the original record and its approved copy with regard to the clinical findings, observations and other activities in the clinical trial, which can be used for reproduction and evaluation of clinical trial. The source documents are documents on which the source data is recorded, including printed, paper or electronic documents.

The subject's medical record and other study related documents (source documents) must be maintained and retained by the Investigator. The Investigator should allow the monitors and auditors/inspectors to review all relevant subject records, including but not limited to the following information:

- Medical/physical condition of the study subject that meets the inclusion criteria prior to participating this study;
- Process of informed consent;
- Operational description of use and implantation of the study product;
- All inspection results and follow-up;
- Examined printed output file or report (for example, X-ray film) that is dated and signed;
- Description of AE and follow-up of AE (description of event, severity, date of occurrence, duration, correlation with the study product, study procedure, outcome, and treatment of the AE, concomitant medications when the AE occurs);
- Description of product complaint;

Confidential Page 78 of 86

03 SEP 2019, VERSION: 1.1

• Study subject's status at the end of the study or withdrawn from the study.

Appropriate source documents must be available for reviewing during the monitoring visit. The Sponsor expects that the study coordinator and/or Investigator will also be available for questions during monitoring visits.

22. FINANCES AND INSURANCE

See the relevant study contract and insurance document.

23. CONFIDENTIALITY

The personal data of the subject participating in the trial is confidential; however, the Ethics Committee, CFDA, competent department of health and family planning, or the Sponsor and its authorized representative may review the personal data of the subject participating in the trial for the purpose of their work according to the local established procedure.

The personal data of the subject should be kept confidential during the entire period of clinical trial, and it should be ensured that the source data can be verified through the supporting information. A unique subject ID number (site number and subject number) will be used to identify all data for every enrolled subject. So long as the data is kept strictly confidential and that the privacy of the subject is ensured to be protected, the data related to this study may be available to third parties (for example, under the audit of regulatory authority).

24. AGREEMENT ON THE PUBLICATION OF TRIAL RESULTS

Following completion of this study, an article might be prepared and published in a scientific journal. No major results or experience from any individual site in this study are allowed to be published before the multicenter trial results are prepared and published. An exception to this rule will need prior approval from the Sponsor. A second publication may be generated by corresponding principal authors. The final analysis and review from all trial data are required to be reviewed and approved by the Sponsor.

Confidential Page 79 of 86

03 SEP 2019, VERSION: 1.1

25. RESPONSIBILITIES THAT EACH PARTY SHOULD BEAR

25.1. Responsibilities of the Sponsor

- 1) The Sponsor is responsible for the initiation, application, organization and monitoring of clinical trial.
- 2) The Sponsor is responsible for the organization to establish and modify the investigator brochure, clinical trial protocol, informed consent form, Case Report Form, relevant standard operating procedure and other relevant documents, carry out the training required for the clinical trial, and provide these documents to the investigators before the study starts.
- 3) The Sponsor should select the qualified trial institution and investigators.
- 4) The Sponsor should sign a written agreement with the clinical trial institution and the Investigator with regard to the clinical trial.
- 5) The Sponsor should provide qualified study product according to the regulatory requirements. The Sponsor should be responsible for the safety of investigational medical product in the clinical trial. The AE, SAE, and the product complaint that may cause an SAE should be collected and reported in accordance with the provisions.
- 6) The Sponsor should inform the regulatory authority at every level when the Sponsor decides to suspend or terminate the clinical trial or at the end of the study.
- 7) The Sponsor should ensure the Investigator conducts the study strictly in compliance with the clinical trial protocol, corrects the protocol deviations in a timely way, and reserves the rights to report, to the regulatory authority, any of issues related to this.
- 8) The Sponsor should bear the treatment cost and relevant economic compensation for the clinical trial-related injury or death of subjects, with the exception of damages due to the fault of medical institution and medical staff in the diagnosis and treatment.
- 9) The Sponsor should select qualified monitors for monitoring and organizing any inspections, as appropriate.

Confidential Page 80 of 86

25.2. Responsibilities of Clinical Trial Institution and Investigator

- 1) The clinical trial institution should evaluate the relevant resources according to the features of investigational medical product prior to the clinical trial, so as to decide whether to participate in this clinical trial.
- 2) The clinical trial institution should properly keep the records and documents of clinical trial according to the agreement with the Sponsor.
- 3) Make sure that the Investigators responsible for the clinical trial have the qualification in accordance with the requirements of related laws and regulations.
- 4) The administrative department for clinical trial of medical product of clinical trial institution should cooperate with the Sponsor to apply to the Ethics Committee and submit the relevant documents prior to the clinical trial according to requirements.
- 5) The Investigator should ensure that the relevant workers participating in the trial have the enough resources and proper training, and keep the training related documents.
- 6) The Investigator should ensure to use the investigational medical product only for the subjects of this clinical trial, and may not charge any fee.
- 7) The Investigator should strictly follow the clinical trial protocol, with the exception of emergency circumstances when the subject faces the direct risk and needs immediate clinical measures, which can be reported later in a written form.
- 8) The Investigator is responsible for recruiting the subjects, communicating with the subject or its legal representative before signing the informed consent.
- 9) The Investigator should protect the rights, safety and health of the subjects.
- 10) In case of an AE occurring in the clinical trial, the Investigator should protect the safety of the subjects and timely report the event to the regulatory authority.
- 11) The Investigator should record all AEs occurring and product deficiencies found in the process of clinical trial, work with the Sponsor to analyze the causes of the events, generate the written analysis report, present the comments on the continuation, discontinuation or termination of the trial, and report to the Ethics Committee by the administrative department for clinical trial of medical product of clinical trial institution for review.
- 12) The Investigator should make sure that the clinical trial data is accurately, completely,

Confidential Page 81 of 86

clearly and timely recorded in the Case Report Form.

- 13) The clinical trial institution and Investigator should make sure that the data, documents and records generated in the clinical trial are timely, true, accurate, clear, and attributable.
- 14) The clinical trial institution and Investigator should accept and cooperate with the monitoring and audit of the Sponsor, the supervision of the Ethics Committee, and the inspection of the Food and Drug Administration, competent department of health and family planning, etc., and provide all required records related to the trial.
- 15) If the clinical trial needs to be suspended or terminated, the subjects should be informed accordingly. It should be ensured that the subjects receive the proper care and follow-up. The clinical trial institution and Investigator should also report this in accordance with the regulations and provide a detailed written explanation. The relevant report should be submitted to the local Food and Drug Administration at the provincial, autonomous regional and municipal level, if necessary.
- 16) The clinical trial institution and Investigator reserve the rights to report to the regulatory authority at every level when the Sponsor violates relevant laws and regulations.
- 17) The Investigator should complete all records and reports at the end of clinical trial. The Investigator should also ensure that the received investigational medical products are properly handled and recorded according to the requirements.

25.3. Responsibilities of other interested parties

See the study related contract, which is available as a separate attachment.

Confidential Page 82 of 86

03 SEP 2019, VERSION: 1.1

26. APPENDICES

26.1. Appendix 1: United States Center for Disease Control (CDC) Guideline for Prevention of SSI Surgical Wound Classification

CLASS I/CLEAN:

An uninfected operative wound in which no inflammation is encountered and the respiratory, alimentary, genital and urinary tracts are not entered. Clean wounds are primarily closed and, if necessary, drained with closed drainage. Operative incisional wounds that follow non-penetrating (blunt) trauma should be included in this category if they meet these criteria.

CLASS II/CLEAN-CONTAMINATED:

An operative wound in which the respiratory, alimentary, genital and urinary tract is entered under controlled conditions and without unusual contamination. Specifically, operations involving the biliary tract, appendix, vagina, and oropharynx are included in this category, provided no evidence of infection or major break in technique is encountered

CLASS III/CONTAMINATED:

Open, fresh, accidental wounds, operations with major breaks in sterile technique or gross spillage from the gastrointestinal tract, and incisions in which acute, nonpurulent inflammation is encountered.

CLASS IV/DIRTY OR INFECTED:

Old traumatic wounds with retained devitalized tissue and those that involve existing clinical infection or perforated viscera. This definition suggests that the organisms causing postoperative infection were present in the operative field before the operation.

Confidential Page 84 of 86

14. SAFETY OUTCOMES	
14.1 SAFETY endpoints	
14.2. Adverse Event	12
14.3. Device Deficiency	12
14.4. Physical Examination	12
14.5. CBC、HGB	13
14.6. Blood Transfusion	13
14.7. Changes from the Protocol Specified Analysis	13

1. Introduction

This document describes the rules and conventions to be used in the presentation and analysis of data for Protocol BIOS_2017_02. It describes the data to be summarized and analyzed, including specifics of statistical analyses to be performed.

This statistical analysis plan (SAP) is based on protocol version 1.1, dated 03/SEP/2019.

2. STUDY OBJECTIVES

The objectives of this 2-arm registration study are to evaluate the safety and to demonstrate non-inferiority of hemostatic effectiveness of SURGICEL Powder compared with SURGICEL Original in controlling mild or moderate parenchymal or soft tissue intraoperative bleeding during general, gynecological, and cardiothoracic surgery in Chinese adult (≥18 years old) subjects.

2.1. EXPLORATORY OBJECTIVES

Demographic information and data collected in this study may be used in Health Economics and Outcomes Research (HEOR). Examples of exploratory data captured in this study include, but are not limited to, estimated blood loss (EBL), blood transfusion (if applicable), drain usage (if applicable), hemoglobin (Hgb) blood testing, and length of stay (LOS).

In addition, data using the surgeon EUQ (Ease of Use Questionnaire), a tool validated in prior clinical trials, will also be collected and analyzed descriptively.

3. STUDY DESIGN

This is a single blind, prospective, randomized, multicenter, multispecialty, controlled clinical study comparing SURGICEL Powder with SURGICEL Original (control arm) as an adjunct to achieve hemostasis in the control of capillary, venous, and small arterial hemorrhage when ligation or other conventional methods of control are impractical or ineffective during surgery (open, laparoscopic, or thoracoscopic) in Chinese adult subjects.

The number of evaluable subjects required for this trial is 210 subjects (105 per treatment arm). In order to account for a potential 10% drop-out rate, at least 234 evaluable subjects (117 per treatment arm) with an appropriate mild or moderate Target Bleeding Site (TBS) will be randomized in a 1:1 allocation ratio to either SURGICEL Powder or SURGICEL Original (control). Randomization will be stratified by investigational site and TBS bleeding severity (mild or moderate bleeding).

Study subjects will be enrolled in approximately 12 study sites. The number of subjects enrolled in any site should not exceed 46 subjects (20% of the total sample size).

After application of either SURGICEL Powder or SURGICEL Original, the TBS will be assessed for hemostasis (no detectable bleeding) at 3, 5, and 10 minutes from application and prior to initiation of final fascial closure on open surgery or port site closure in laparoscopic or thoracoscopic surgical procedures.

All enrolled subjects will be followed post-operatively through discharge, and via phone call or office visit at 30 days (+14 days) post-surgery. In addition, all enrolled subjects will receive a 6-month (+/-30 days) follow-up phone call or office visit to assess the occurrence of any SAE requiring surgical intervention and assessed as possibly related, probably related, or related to the study treatment.

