3.2. Contents of the Clinical Trial

This is a single blind, randomized, prospective study comparing SURGICEL Powder with SURGICEL Original (control) as an adjunct to achieve hemostasis in the control of capillary, venous, and small arterial hemorrhage when ligation or other conventional methods of control are impractical or ineffective during surgery (open, laparoscopic, or thoracoscopic) in Chinese adult subjects.

Prospective subjects will be informed about the nature of the research, given the informed consent form (ICF) to read, and, if he/she understands the content, will be asked to provide consent by signing the ICF.

Screening and enrollment will continue until at least 234 evaluable subjects from approximately twelve (12) investigational sites, with an appropriate mild or moderate Target Bleeding Site (TBS) are randomized into the study. The TBS will be the only region evaluated for the primary endpoint and all secondary effectiveness endpoints.

All enrolled subjects will be followed post-operatively through discharge, and via phone call or office visit at 30 days (+14 days) post-surgery. In addition, all enrolled subjects will receive a 6-month (+/-30 days) follow-up phone call or office visit to assess the occurrence of any serious adverse event (SAE) requiring surgical intervention and assessed as possibly related or related to the study treatment.

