10. OVERALL DESIGN

10.1. Trial Design

This is a single blind, prospective, randomized, multicenter, multispecialty, controlled clinical study comparing SURGICEL Powder with SURGICEL Original as an adjunct to achieve hemostasis in the control of capillary, venous, and small arterial hemorrhage when ligation or other conventional methods of control are impractical or ineffective during surgery (open, laparoscopic or thoracoscopic) in Chinese adult (≥18 years old) subjects.

At least 234 evaluable subjects with an appropriate mild or moderate TBS will be randomized in a 1:1 allocation ratio to either SURGICEL Powder or SURGICEL Original (control).

After application of either SURGICEL Powder or SURGICEL Original, the TBS will be assessed for hemostasis (no detectable bleeding) at 3, 5, and 10 minutes from application and prior to initiation of final fascial closure on open surgery or port site closure in laparoscopic or thoracoscopic procedures.

All enrolled subjects will be followed post-operatively through discharge, and via phone call or office visit at 30 days (+14 days) post-surgery. In addition, all enrolled subjects

Confidential Page 42 of 86

ETHICON, LLC. BIOS_2017_02

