13. STATISTICAL CONSIDERATIONS

13.1. Analysis Sets

The following three analysis sets are defined:

Confidential Page 62 of 86

- Intent-to-Treat (ITT) analysis set consists of all subjects for whom TBS was identified. Subjects who do not complete the procedure after TBS identification will be included in the ITT.
- Per-Protocol (PP) analysis set (set of evaluable subjects) consists of all ITT subjects who have no major protocol deviations and have data available for primary effectiveness endpoint.
- Safety analysis set consists of all subjects who received study product.

The primary effectiveness endpoint will be analyzed using the ITT and the PP sets. However, the primary analysis will be based on the PP set. The ITT analysis will be considered supportive.

All secondary effectiveness endpoints will be analyzed using the ITT set, while safety endpoints will be analyzed using the Safety set.

It is not anticipated that there will be data missing for the primary or secondary effectiveness endpoints, but, if there is, the analyses based on the ITT set will consider missing data as failures for these endpoints. Missing data for safety endpoints will not be imputed.

Major protocol deviations are deviations that have an impact on the primary effectiveness endpoint. These will be determined prior to database lock.

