13.2. Statistical Design, Method and Analysis Procedure

This is a single blind, randomized, prospective study comparing SURGICEL Powder with SURGICEL Original (control) as an adjunct to achieve hemostasis in the control of capillary, venous, and small arterial hemorrhage when ligation or other conventional methods of control are impractical or ineffective during surgery (open, laparoscopic, or thoracoscopic) in Chinese adult patients.

Subjects will be randomly assigned to either SURGICEL Powder (Test) or SURGICEL Original (Control) in a 1:1 allocation ratio. Randomization will be stratified by investigational site and TBS bleeding severity (mild or moderate bleeding).

Two analyses will be performed. The first analysis will occur after all subjects complete phone call or office visit [30 days (+ 14 days) post-surgery]. All data collected through 30-day (+14 days) follow-up will be analyzed. The second analysis will occur after all subjects complete phone call or office visit [6-month (+/-30 days) post-surgery] and the data collected at this follow-up is available. The second analysis will be performed on the data from the 6-month follow-up assessing any occurrences of SAEs requiring surgical intervention and assessed as possibly related or related to the randomized study treatment.

Confidential Page 63 of 86

The **primary effectiveness endpoint** is defined as the proportion of subjects achieving hemostatic success at 5 minutes following the application of SURGICEL Powder or SURGICEL Original with no re-bleeding requiring additional treatment at the TBS any time prior to initiation of final fascial closure.

This is a non-inferiority trial with a 10% margin and the statistical analysis comparing treatment groups for primary effectiveness endpoint performed at one-sided significance level of 0.025 and 80% power. The true success rates are assumed to be 85% in the SURGICEL Powder (Test) group and 80% in the SURGICEL Original (Control) group. 14, 15, 16, 17. For the justification of the assumed success rates in the two treatment groups, see Section 7.

Study Hypothesis

The statistical hypothesis for testing the treatment group difference for primary effectiveness endpoint is presented as follows:

• H_0 : P_T – $P_C \le -0.1$ tested against the alternative hypothesis

 H_1 : $P_T - P_C > -0.1P_C$ proportion of successes in Control group, and P_T is the proportion of successes in Test group.

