13.3. Calculation of Sample Size

13.3.1. Total Sample Size

The number of evaluable subjects required for this trial is 210 subjects (105 per treatment arm). In order to account for a potential 10% drop-out rate, at least 234 subjects (117 per treatment arm) will be randomized into the trial in a 1:1 allocation ratio SURGICEL Powder to SURGICEL Original.

Two hundred and ten (210) evaluable subjects (105 per study arm) will achieve 80% power to detect a non-inferiority margin difference in group proportions of 0.1 using a Farrington-Manning score test with a one-sided significance level of 0.025. The proportion of successes in the Control group is assumed to be 0.8. The proportion of successes in Test group is assumed to be 0.7 under the null hypothesis of inferiority. The power was computed for the case when the actual proportion of successes in the Test group is 0.85.

13.3.2. Minimum and Maximum Number of Subjects in Each Clinical Trial Institution and Reasons for Determination

A total of 234 subjects will be enrolled in approximately 12 study sites. The number of subjects enrolled in any site should not exceed 46 subjects (20% of the total sample size).

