13.4. Significance Level and Power of Clinical Trial

The power of the statistical test at which the sample size for the primary endpoint was calculated is 80%, and the one-sided significance level of the test was set to 0.025.

For the primary effectiveness endpoint, a one-sided 97.5% confidence interval for P_T - P_C will be constructed using the Farrington-Manning (FM) score method. In addition, two-sided 95% confidence intervals for the proportion of successes in each treatment group separately will be constructed using the Clopper-Pearson method.

For the binary (success/failure) secondary effectiveness endpoints (3 and 10 minutes hemostasis endpoints), within-treatment group two-sided 95% confidence intervals will be reported for the proportion of successes using the Clopper-Pearson method. A two-sided 95% confidence interval for the difference in proportion of successes between treatment groups (Test minus Control) will also be calculated for each binary secondary effectiveness endpoint using the FM score method.

Confidential Page 66 of 86

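### Does the plan call for 234 evaluable subjects, and so for about 26 more randomised than the sample-size section provides?

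*SAP*

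**What the plan says.** The sample-size text is consistent. Protocol 13.3.1 requires 210 evaluable subjects (105 per arm) and, to allow for 10% drop-out, states that "at least 234 subjects (117 per treatment arm) will be randomized into the trial". The synopsis and Protocol 10.1.11 give the same pair of numbers: 210 evaluable, 234 randomised.

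Three other sentences put the word evaluable beside 234:

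- Protocol 3.2: "Screening and enrollment will continue until at least 234 evaluable subjects from approximately twelve (12) investigational sites". The sentence goes on to say that these subjects, having a suitable mild or moderate bleeding site, are randomised into the study.
- Protocol 10.1: "At least 234 evaluable subjects with an appropriate mild or moderate TBS will be randomized in a 1:1 allocation ratio".
- SAP section 3: "at least 234 evaluable subjects (117 per treatment arm) with an appropriate mild or moderate Target Bleeding Site (TBS) will be randomized". The sentence just before it gives 210 as the evaluable number required.

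Evaluable has a defined meaning. Protocol 13.1 reads "Per-Protocol (PP) analysis set (set of evaluable subjects) consists of all ITT subjects who have no major protocol deviations" and adds that data for the primary endpoint must be available. SAP 5.3 keeps the link between evaluable and PP. The PP set carries the primary analysis.

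**The concern.** If evaluable means PP, the documents state the size of the primary analysis set in two ways: 210 in the sample-size section and 234 in the design sections. Protocol 3.2 matters most because it says when enrolment ends. Taken literally, a sponsor who stopped at 234 randomised would miss that target as soon as one subject left the PP set, and would have had to randomise about 260 to meet it. The rule also could not be applied during enrolment, because major deviations are settled only before database lock. At stake would be the number of patients exposed, the power of the primary analysis, and an apparent shortfall against the plan in a registration trial.

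**Working it through.** **Inputs.** Control success 0.80, test success 0.85 and 1:1 allocation (Protocol 13.3.1). The test is specified as "using a Farrington-Manning score test with a one-sided significance level of 0.025". Power is 80% (13.4) and drop-out 10% (13.5). On the margin, Protocol 13.2 says "This is a non-inferiority trial with a 10% margin".

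**1. Reproduce the evaluable number.** The restricted estimates under a difference of −0.10 are 0.7597 (test) and 0.8597 (control).

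- s0 = √(0.7597 × 0.2403 + 0.8597 × 0.1403) = 0.5506
- s1 = √(0.85 × 0.15 + 0.80 × 0.20) = √0.2875 = 0.5362
- n per arm = [(1.960 × s0 + 0.8416 × s1) / (0.85 − 0.80 + 0.10)]² = 104.1, rounded up to **105**, so 210 in total. This matches the protocol.

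**2. Reproduce the randomised number.** 210/0.9 = 233.3; 105/0.9 = 116.7 per arm, rounded up to 117, so **234**. This matches. In reverse, 234 × 0.9 = 210.6, which covers the 210.

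**3. Size of the literal reading.** If 234 had to be evaluable, 234/0.9 = **260** randomised (130 per arm), 26 more than 234. Power = Φ{[0.15√n − 1.960 × s0] / s1}:

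| Evaluable per arm | Power, FM formula | Power, exact enumeration |
|---|---|---|
| 105 | 80.3% | 81.3% |
| 117 | 84.5% | 85.3% |

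The stated 80% matches 105 evaluable per arm.

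**4. Which reading fits the rest of the plan?**

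| Statement | 234 randomised | 234 evaluable (260 randomised) |
|---|---|---|
| Synopsis, Protocol 10.1.11 and 13.3.1: 210 evaluable, 234 randomised | fits | contradicts |
| SAP 3: 234 is the figure that allows for 10% drop-out | fits | contradicts |
| Protocol 10.1.7: withdrawals not replaced, 10% attrition already included | fits | the 234 would have no allowance in it |
| Protocol 13.3.2 and 15.2: total enrolment 234 | fits | contradicts |
| Protocol 13.3.2 and SAP 3: site cap 46, being 20% of the total | 0.20 × 234 = 46.8 | 0.20 × 260 = 52 |
| Verb in Protocol 3.2, 10.1 and SAP 3: the 234 are or will be randomised | fits | PP status is unknown at randomisation |

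Every line of the comparison favours 234 randomised.

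**The case for a change.** The strongest case for a correction is that evaluable is not a loose adjective here. Both documents equate it with the set used for the primary analysis, and Protocol 3.2 uses it in the sentence that governs when enrolment stops. SAP section 3 gives 210 and 234 as evaluable counts in consecutive sentences, and both cannot be right. SAP 14.7 revised the PP definition without removing the conflict. Deleting one word in three places would cost almost nothing and would spare an auditor a query.

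The textual point stands: the word is misapplied, and in current text. The claim that the enrolment target is wrong does not. The Protocol 3.2 sentence is completed by randomisation of subjects with a suitable bleeding site, an event that can be counted on the day. That an evaluable-based stop could not be operated is better evidence that PP status was never meant there than evidence of a second defect. In context the word most naturally describes eligible subjects with an assessable bleeding site. Even the literal reading would lead to more subjects and more power. It would not weaken the non-inferiority test.

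**Conclusion.** This is a clerical slip. The intended design, 210 evaluable from 234 randomised, is stated in the synopsis, Protocol 10.1.11 and 13.3.1, reproduces by calculation, and agrees with the no-replacement rule, the total enrolment and the site cap. A sponsor working from the sample-size section enrols the right number, and the primary analysis has the stated power: 80.3% by formula at 105 per arm. The difference of 26 subjects and about 4 percentage points of power (84.5 − 80.3 = 4.2) arises only if one adjective overrides all the other statements of the target.

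Removing the word would alter no sample size, margin, error rate, analysis set or decision rule, so it is not a reason to change the plan. This rests on the plan's own assumptions: success rates of 85% and 80%, and a 10% loss between randomisation and the PP set. Whether 10% is a realistic loss is a separate question that the wording does not affect.
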